10.2 A written consent is obtained. (Appendix E)

10.3 The patients' demographic data and medical history will be obtained by conducting an interview and a physical examination.

10.4 In the first interview, patient will also be asked to complete a questionnaire on the gastrointestinal symptoms, stool consistency and severity of constipation.

Patients will be given 7 days' supply of placebo or probiotics, which patient are required to take each sachet of Hexbio® or placebo twice per day for 7 days.

10.5 A training of using the daily stool dairy will be done at the beginning of study. Upon completion (day 7) the dairy will be collected and data will be analyzed.

FLOW CHART

[figure not shown]

Figure 1. Flow chart of the study methodology.

GLOSSARY OF TERMS

1. Probiotics

Living microorganisms that enter the gastrointestinal tract in an active form in sufficient numbers to exert positive effect.

2. Constipation

A condition in which there is difficulty in emptying the bowels, usually associated with hardened feces.

3. Functional Constipation

A condition that fulfill the **Rome III criteria for functional constipation**.

Refer to Appendix A

4. Bristol Stool

A medical aid designed to classify the form of human feces into seven categories. Refer to Appendix B

5. Advanced Chronic Illness

An occurring when one or more conditions become serious enough that general health and functioning decline, and treatments begin to lose their impact.

6. Colony Forming Unit (CFU)

[figure not shown]
A unit used to estimate the number of viable bacteria or fungal cells in a sample.

APPENDIX A

List of medical illness associated with constipation.

1. Diabetes Mellitus
2. Hypertension
3. Chronic Kidney disease
4. Chronic Lung disease
5. Chronic Heart Failure
6. Hypothyroidism
7. Scleroderma
8. Hyperparathyroidism
9. Uraemia
10. Hypocalcaemia
11. Hypokalaemia

APPENDIX B

DAILY STOOL DIARY						LIKERT SCALE / NUMERIC PAIN RATING SCALE							
Study No: _____ Patient's Sticker: _____ EVALUATING THE EFFECT OF PROBIOTICS IN CHRONIC CONSTIPATION ELDERLY PATIENTS WITH MULTIPLE CO-MORBIDITIES													
DAY	CONSTIPATION RELATED SYMPTOMS					BRISTOL STOOL CHART							
	STRAINING	PAINFUL EVACUATION	BLOATING & FLATULENCE	STOMACH CRAMPS	OTHERS		TYPE 1	TYPE 2	TYPE 3	TYPE 4	TYPE 5	TYPE 6	TYPE 7
BEFORE													
1													
2													
3													
4													
5													
6													
7													

Instructions: Please fill up the boxes according to likert scale for the constipation related symptoms and mark 'X' for the Bristol stool chart.

Bristol chart adapted from http://www.cbc.ca/stevenandchris/content/images/poop_101_1.jpg

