8.2 Safety

Patients will be counseled that generally safety profile of probiotics seems to be good. Based on the available trials, no adverse effects were noted. There might be a concern issue of safety in immune-compromised patients or those critically ill, which they will be excluded in this study.

Patients will be withdrawn from the study if they experience intolerable or any possible excessive side effects due to probiotics.

9. Assessment variables and methods of assessing.

9.1 Targeted patients will be assessed with a questionnaire (Appendix C) on gastrointestinal symptoms, well-being and stool habits. The stool consistency will be scored by a seven-point scale according to the Bristol Stool Form Scale (Appendix B). Severity of constipation will be categorized into four groups (severe, moderate, mild and no symptoms). Symptoms specifically

related to constipation such as bloating and flatulence will be recorded in detail. Severity of symptom is measured by Likert score of frequency (Very frequently, frequently, occasionally, rarely and never).

9.2 Each individual patient will be required to fill in the questionnaire at the beginning of the trial. Subsequently, patient will be required to fill up the stool chart and recorded their symptoms in a given dairy daily during the study period. Training on how to use and record the dairy will be conducted upon embarking into the study. A contact number will be advised to the participants to aid their understanding. The dairy will be collected at day 7 upon completion of the study.

Other assessment

1. Assessment of the presence of underlying medical illness will be done at the initial presentation, assessed by questionnaire about the medical history and physical examination.

10. Study conduct

10.1 Elderly patients attending medical/surgical clinics or being admitted to the medical/surgical wards PPUKM will be screened. Those with underlying medical illnesses and suspected to have constipation are selected. Random selection of the participants either for intervention group or control will be pre-determining during screening.

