APPENDIX D

[figure not shown]
EVALUATING THE EFFECT OF PROBIOTICS IN CHRONIC CONSTIPATION ELDERLY PATIENTS WITH MULTIPLE CO-MORBIDITIES

QUESTIONNAIRES

[figure not shown]
Study Number:

Patient's Sticker:

[figure not shown]
1. How frequent is your bowel movements per week?

[figure not shown]
2. Do you need assistance in evacuation? (enema/digital-manual maneuvers)

[figure not shown]
3. Do you have sensation of anorectal obstruction/ blockage?

[figure not shown]
4. Feeling of incomplete evacuation?

[figure not shown]
5. Do you have lumpy or hard stools?

[figure not shown]
6. Any straining or squeezing on defecation attempts?

[figure not shown]
1. How long have you had constipation?

[figure not shown]
2. Do you have bloating in your stomach?

[figure not shown]
3. Do you have flatulence?

[figure not shown]
4. Do you have stomach cramps?

[figure not shown]
5. How many unsuccessful attempts of evacuation within 24hours?

6. Do you have abdominal pain?

7. How long do you spend in the lavatory per attempt? (minutes)

Statistical analysis Plan

The collected data was analysed using IBM SPSS Statistics for Windows version 21.0 software (IBM Corp., Armonk, NY, USA) and Microsoft Office Excel 2010software (Microsoft, Redmond, WA, USA). Statistical significance was set at $p = <0.050$.

All of the data was assessed for normality via the usual processes.

The baseline characteristic differences between the two groups were evaluated using the Mann-Whitney U and chi-squared tests. The median results of the improvement in stool frequencies and stool consistency between the treatment and placebo group were compared using the Mann-Whitney U test. The constipation-related symptom improvements were analysed using the chi-squared test.

Intention to treat analysis was used in this trial, where only the final results within the group which they were randomized, receiving the treatment and completed the treatment assignment were analysed. Participants who deviates from the protocol as being non-compliance or withdrew consent were not included into the analysis.

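### The diary, the only on-treatment symptom record, scores bloating and flatulence in one shared box with no scoring rule, so separate changes cannot be estimated and divergent changes may be masked

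*Combined protocol and SAP*

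**What the plan says.** - **Appendix B, daily stool diary.** There are five symptom columns: straining, painful evacuation, "BLOATING & FLATULENCE", stomach cramps and others. Each has a BEFORE row and rows for days 1 to 7. The instruction is "Please fill up the boxes according to likert scale for the constipation related symptoms"; nothing is added for the shared column.
- **Section 9.1.** Symptoms "related to constipation such as bloating and flatulence will be recorded in detail". Severity is graded on five frequency levels: "Very frequently, frequently, occasionally, rarely and never".
- **Appendix D.** Two separate items: "Do you have bloating in your stomach" and "Do you have flatulence".
- **Section 9.2.** "Each individual patient will be required to fill in the questionnaire at the beginning of the trial"; the diary is kept from then on and collected at day 7. Sections 10.4 and 10.5 give the same sequence.
- **Section 8.1.** Daily scoring of constipation-related symptoms over the 7 study days is part of the primary end point.
- **Statistical analysis plan.** Symptom improvement is compared by a chi-squared test. Improvement is not defined and no individual symptom is named.

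**The concern.** Section 9.1 names two symptoms as examples of those needing detailed recording, and they are the two that the diary merges. Straining, painful evacuation and stomach cramps each have their own column. Appendix D treats bloating and flatulence as distinct, but only at baseline.

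A patient whose bloating eases while flatulence does not has one box to fill. The patient may enter the worse symptom, the milder one or something in between, and different patients may choose differently. Section 9.2 promises training in the diary but states no rule for this case. What is at stake is one component of the daily symptom scoring inside the primary end point. An effect on one of the two symptoms could be diluted or hidden, and the data cannot be separated once collected.

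**Working it through.** The documents give no sample size, event rate or effect size for symptoms, so there is no figure of the plan's to reproduce. The check has three parts.

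**1. Is there any other on-treatment record?** Section 9.1 labels the questionnaire Appendix C, but the bloating and flatulence items are printed in Appendix D. Sections 9.2 and 10.4 place the questionnaire at the start, and no repeat is described. The diary is the only symptom record after that.

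**2. What does one box lose in a single patient?** Assume the five levels are coded 0 to 4 (B = bloating, F = flatulence) and that the patient enters the mean, the worse or the milder of the two.

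| Case | True change B, F | Box: mean | Box: worse | Box: milder |
|---|---|---|---|---|
| B 3→1, F 1→3 | −2, +2 | 0 | 0 | 0 |
| B 3→1, F 1→2 | −2, +1 | −0.5 | −1 | 0 |
| B 3→1, F 2→2 | −2, 0 | −1 | −1 | −1 |
| B 4→1, F 3→2 | −3, −1 | −2 | −2 | −2 |

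Equal and opposite changes vanish in this example. Unequal opposite changes vanish only under some habits. A change in one symptom alone, or unequal changes in the same direction, are blended and do not cancel. In all four cases the two true changes cannot be recovered from the box.

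**3. What could this do to the group comparison?** All inputs are assumed: bloating improves in 60% (probiotic) v 40% (placebo), flatulence in 40% v 40%, the two are independent, n = 100 per arm, two-sided 5% (the plan states 0.05 but not the sidedness).

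Power ≈ Φ[(d − 1.96·s0)/s1], where d is the difference in proportions, s0 = √[2p̄(1−p̄)/n] and s1 = √[(p1(1−p1) + p2(1−p2))/n]. The opposite tail is negligible in these cases.

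- **Bloating in its own box:** 60% v 40%, d = 0.20. (0.20 − 1.96×0.0707)/0.0693 = 0.89, power 81%.
- **Box improves only when both do** (for example, worse-of-two scoring from equal baselines): 0.6×0.4 = 24% v 0.4×0.4 = 16%, d = 0.08. (0.08 − 1.96×0.0566)/0.0563 = −0.55, power about 29%.
- **Box improves when either does:** 1 − 0.4×0.6 = 76% v 1 − 0.6×0.6 = 64%, d = 0.12. (0.12 − 1.96×0.0648)/0.0642 = −0.11, power about 46%.
- **Worse symptom entered, bloating clearly worse at baseline in every patient:** the box follows bloating, so 60% v 40% and 81% are kept.
- **Worse symptom entered, bloating clearly worse in half and tied in half:** 0.5×60 + 0.5×24 = 42% v 0.5×40 + 0.5×16 = 28%, d = 0.14. (0.14 − 1.96×0.0675)/0.0667 = 0.12, power about 55%.
- **Worse symptom entered, flatulence clearly worse in every patient:** the box follows flatulence, 40% v 40%, so the bloating effect does not appear.

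**The case against.** The best defence is that no planned analysis is broken. The analysis plan names neither symptom, section 9.1 mentions them together as examples, and a combined gas item is a common instrument choice. The BEFORE row also gives that item a like-for-like baseline on the same form, so change to day 7 needs no match to Appendix D. If the two symptoms move together, little is lost.

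Much of this stands. The merged item is reportable, and the mismatch with Appendix D does not invalidate its change score. But the plan does not declare a composite or say how to score one, so the BEFORE entry is as ambiguous as the later ones. The promise of detailed recording in section 9.1 is also not met by one box for two symptoms.

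Three stronger readings are tempting and are not supported:

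- A reader might infer that any opposite or unequal changes cancel. The single-patient cases show that same-direction changes blend, and that opposite changes cancel only for some scores and habits.
- A reader might infer that neither symptom can be reported at all. Each is asked separately at baseline, and the combined item can be followed throughout.
- A reader might infer that power must fall to 29%, or that the product moves the two symptoms in opposite directions. The first is one scoring case among several. The documents offer nothing for the second.

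**Conclusion.** The point holds as a limited measurement defect. Because the only on-treatment record merges the two symptoms without a scoring rule, a separate change in bloating or in flatulence cannot be estimated by any analysis, and divergent changes may be masked or blended.

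The size cannot be fixed from the documents. Under the assumed rates, the loss of a 20-point bloating effect runs from none to all of it, according to how patients fill the box and which symptom is worse at the start. The two simple rules, both improve or either improves, leave 8 and 12 points. These figures also rest on independence of the two symptoms and on 100 per arm, neither of which the plan states.

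Severity is minor: this is one of five symptom columns, in a primary end point that also covers stool output and consistency. It still merits a change because the remedy is cheap and the loss is permanent once diaries are filled.

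**What to change.** Split the Appendix B column into BLOATING and FLATULENCE, each with its own BEFORE box and day 1 to 7 boxes, and report them as two symptoms in line with the two Appendix D items. This costs the patient one more box per day and the analysis one more symptom comparison. It needs no extra visit or staff.

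A cheaper but weaker alternative is to keep one column, declare it a composite, and add a one-line scoring rule to the diary instruction and the training already planned. That removes the ambiguity but does not recover separate changes.

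If diaries are already completed, neither change can be applied to the data. Report the item as a combined bloating/flatulence symptom measured from the BEFORE row, make no separate claim for either symptom, and state the limitation.

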APPENDIX C

EVALUATING THE EFFECT OF PROBIOTICS IN CHRONIC CONSTIPATION ELDERLY PATIENTS WITH MULTIPLE CO-MORBIDITIES

Data Collection Form

Study Number:

Patient's Sticker:

Socio-demography:

Age:

Gender: Male / Female

Ethnic : Malay / Indian / Chinese/ Others (please state: _____)

Clinical characteristic

Medical illness:

If yes, please tick:

	Durations (years)
Diabetes Mellitus	()
Asthma	()
Hypertension	()
Dyslipidaemia	()
Chronic Kidney disease	()
Others (please specify): _____	()
	()

Symptoms associated with constipation:

(*at least in 25% of defecations – Rome III diagnostic criteria of functional constipation)

If yes, please tick:

Straining	()
Lumpy or hard stools	()
Sensation of incomplete evacuation	()
Sensation of anorectal obstruction/ blockage	()
Manual maneuvers to facilitate defecations	()
Fewer than 3 defecations per week	()

Duration: _____ months/ years

Previous treatment:

frequency:

Laxatives	()	() days/months/years
Probiotics	()	() days/months/years
High fibre diets	()	() days/months/years
Enemas	()	() days/months/years

APPENDIX D

[figure not shown]
EVALUATING THE EFFECT OF PROBIOTICS IN CHRONIC CONSTIPATION ELDERLY PATIENTS WITH MULTIPLE CO-MORBIDITIES

QUESTIONNAIRES

[figure not shown]
Study Number:

Patient's Sticker:

[figure not shown]
1. How frequent is your bowel movements per week?

[figure not shown]
2. Do you need assistance in evacuation? (enema/digital-manual maneuvers)

[figure not shown]
3. Do you have sensation of anorectal obstruction/ blockage?

[figure not shown]
4. Feeling of incomplete evacuation?

[figure not shown]
5. Do you have lumpy or hard stools?

[figure not shown]
6. Any straining or squeezing on defecation attempts?

[figure not shown]
1. How long have you had constipation?

[figure not shown]
2. Do you have bloating in your stomach?

[figure not shown]
3. Do you have flatulence?

[figure not shown]
4. Do you have stomach cramps?

[figure not shown]
5. How many unsuccessful attempts of evacuation within 24hours?

6. Do you have abdominal pain?

7. How long do you spend in the lavatory per attempt? (minutes)

Statistical analysis Plan

The collected data was analysed using IBM SPSS Statistics for Windows version 21.0 software (IBM Corp., Armonk, NY, USA) and Microsoft Office Excel 2010software (Microsoft, Redmond, WA, USA). Statistical significance was set at $p = <0.050$.

All of the data was assessed for normality via the usual processes.

The baseline characteristic differences between the two groups were evaluated using the Mann-Whitney U and chi-squared tests. The median results of the improvement in stool frequencies and stool consistency between the treatment and placebo group were compared using the Mann-Whitney U test. The constipation-related symptom improvements were analysed using the chi-squared test.

Intention to treat analysis was used in this trial, where only the final results within the group which they were randomized, receiving the treatment and completed the treatment assignment were analysed. Participants who deviates from the protocol as being non-compliance or withdrew consent were not included into the analysis.

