Official Title of the study:

Evaluation of the efficacy of probiotics in treating constipation in elderly patients with multiple chronic co-morbidities: a randomized control trial

NCT no: Nil

Date of Document:

22nd July 2019

Study Protocol

1. Study design

This is a randomized double-blinded clinical trial study.

2. Study population and subjects

Background and selection of study centers

The study will be conducted at the outpatient clinics, medical and surgical wards in Universiti Kebangsaan Malaysia Medical Centre.

3. Target population

- 3.1 The target populations are older patients aged 60 years or above with at least 2 chronic medical illnesses (Appendix A) and who complain of constipation that persists for several weeks or longer.
- 3.2 These patients are those who attending the medical/surgical outpatient clinics or being admitted to the medical/surgical wards in UKM Medical Centre during the study period.

The participants will be assigned to either interventional group or control randomly and the random selection is pre-determined prior to recruitment.

4 Inclusion criteria.

- 4.1 Elderly patients aged 60 years or above and able to give consent.
- 4.2 Patients who complain of constipation as per Mayo's clinic definition:
"Infrequent bowel movements of fewer than three bowel movements per week or difficult passage of stools that persists for several weeks or longer". (13)
- 4.3 Patients who have at least 2 chronic illnesses such as Diabetes Mellitus, Hypertensions, Chronic Kidney disease, Chronic Lung disease, or any medical illness which are prone to have constipation.

5. Exclusion criteria.

- 5.1 Patients with constipation of organic cause such as colorectal carcinoma, colonic ischaemia, inflammation, post radiation stricture, obstruction or presence of external compression.
- 5.2 Patients with constipation of neurological causes such as cerebrovascular disease and stroke, Parkinson's disease, autonomic neuropathy and spinal cord lesions.
- 5.3 Patients who are taking calcium supplements more than 1500mg a day.
- 5.4 Patients who are immune-compromised or critically ill.
- 5.5 Patients who are on opioid analgesia.
- 5.6 Patients with psychiatric illness.
- 5.7 Patients who are on any form of medications at point of entering the study that altered the normal bowel movement (either decreasing or increasing the peristalsis of the gut)
- 5.8 Patients who refuse to enter or consent for the study.

6. Subject withdrawal and Drop out

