8.1 Primary end point

A completed questionnaire on patient's demographic and medical illness data, stool output/day, stool consistency per output/day and constipated related symptoms scoring/day over the period of 7 study days.

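### Stool frequency and consistency get an unadjusted Mann-Whitney test with no between-arm estimate or interval, although a baseline for each is collected and could be used at almost no cost

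*Combined protocol and SAP*

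**What the plan says.** The Statistical analysis Plan, third paragraph, says that "The median results of the improvement in stool frequencies and stool consistency between the treatment and placebo group were compared" by the Mann-Whitney U test, judged against a 0.05 threshold. Its only other use of baseline is that "The baseline characteristic differences between the two groups were evaluated using the Mann-Whitney U and chi-squared tests".

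The outcome data (section 8.1) are "stool output/day, stool consistency per output/day and constipated related symptoms scoring/day over the period of 7 study days". For consistency, section 9.1 says: "The stool consistency will be scored by a seven-point scale according to the Bristol Stool Form Scale".

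Baselines are recorded as follows:
- **Frequency:** Appendix D question 1 asks "How frequent is your bowel movements per week". Section 9.2 has every patient complete the questionnaire at the start; I take this to include Appendix D.
- **Consistency:** section 10.4 says "In the first interview, patient will also be asked to complete a questionnaire on the gastrointestinal symptoms, stool consistency and severity of constipation". The Appendix B diary also has a BEFORE row above days 1 to 7, with the instruction "Please fill up the boxes according to likert scale for the constipation related symptoms and mark 'X' for the Bristol stool chart".

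Section 4.2 admits patients with "fewer than three bowel movements per week or difficult passage of stools that persists for several weeks or longer", so baseline frequency is not confined to low values.

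The documents do not define improvement. They name no covariate, between-arm estimate or interval, and give no sample size, target effect, SD or baseline-to-follow-up correlation.

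**The concern.** Two medians and a p-value do not tell a reader how many stools per week separate the arms, or what a non-significant result rules out. As no sample size calculation is shown, an interval is the only way to judge the trial's precision.

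The second issue is how baseline is used. Subtracting it over-corrects when baseline and follow-up are weakly correlated. Ignoring it under-corrects when they are strongly correlated. Rank ANCOVA estimates the correction from the data, so the correlation need not be guessed. Significance tests on baseline characteristics adjust nothing.

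**Working it through.** **Inputs.** From the documents: two arms, 0.05 threshold, 7-day outcomes, a baseline for each measure, two entry routes. Assumed: two-sided testing, 1:1 allocation, 75 per arm, rate ratio 1.35, and all distributions and correlations. The plan has no figure of its own to reproduce.

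**Large-sample formula.** Let r be the baseline-to-follow-up correlation and k = baseline SD / follow-up SD. With follow-up variance set to 1, the variances are:
- 7-day value alone: 1
- change: 1 + k² - 2rk
- ANCOVA: 1 - r²

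Change minus ANCOVA is (k - r)², so linear adjustment matches the change score only when r = k. Starting from an assumed 80% power, power after adjustment is Φ((1.960 + 0.842)/√ratio - 1.960). Against change with k = 1:
- r = 0.1: ratio 0.99/1.80 = 0.55, power 96.5%
- r = 0.7: ratio 0.51/0.60 = 0.85, power 86.0%

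With k cut to 0.3-0.5, power is only 80.0-85.5% for r = 0.1-0.5.

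**Simulated power, frequency.** Poisson counts with lognormal patient effects, baseline/follow-up means 2.5/4.0 or 3.0/3.0, 5,000 runs, Quade rank ANCOVA. Power in %; gains are differences between columns.

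| Setting | rho, k | Change | 7-day alone | Rank ANCOVA | Gain v change | Gain v 7-day |
|---|---|---|---|---|---|---|
| Any baseline | 0.12, 0.72 | 67.1 | 78.2 | 78.5 | +11.4 | +0.3 |
| Any baseline | 0.32, 0.72 | 77.8 | 77.8 | 81.1 | +3.3 | +3.3 |
| Any baseline | 0.13, 1.00 | 47.3 | 65.6 | 66.1 | +18.8 | +0.5 |
| Any baseline | 0.32, 1.00 | 56.8 | 67.2 | 70.7 | +13.9 | +3.5 |
| High correlation | 0.51, 0.64 | 72.3 | 62.7 | 68.8 | -3.5 | +6.1 |
| High correlation | 0.64, 0.70 | 82.2 | 66.4 | 77.4 | -4.8 | +11.0 |
| High correlation | 0.67, 0.71 | 88.5 | 69.0 | 84.7 | -3.8 | +15.7 |
| High correlation | 0.56, 1.00 | 64.7 | 56.1 | 66.9 | +2.2 | +10.8 |

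If everyone enters below 3 per week (rho 0.05-0.12, k 0.30-0.39), the gain over change is 0.8 to 3.8 points. Runs at nearby settings gave +6 to +23 points with unrestricted entry at rho 0.07-0.28, +1 to +5 with restricted entry, and a loss of about 5 at rho 0.63-0.69, including at k = 1.0. The linear formula cannot produce that loss; it arises with ranked counts.

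Baseline reliability matters as well. At 50 per arm with unrestricted entry, the gain over change is 64.0 - 66.4 = -2.4 points with accurate recall and 53.0 - 45.4 = +7.6 with noisy recall.

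**Consistency** (latent shift 0.45 SD, k 0.83). Change / 7-day alone / rank ANCOVA: 60.6/73.9/75.1 at rho 0.19 and 92.0/74.3/92.4 at rho 0.65.

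**False positives.** Over all simulated trials, type I error is 4.1-5.8% for all three tests. Baseline differences above 1.5 SE occur in 2 × (1 - Φ(1.5)) = 13.4% of trials under normality, and in roughly 13-16% as simulated. Within those trials, the frequency rates with unrestricted entry are:

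| rho, k | Change | 7-day alone | Rank ANCOVA |
|---|---|---|---|
| 0.12, 0.72 | 13.2 | 5.3 | 5.1 |
| 0.32, 0.72 | 8.6 | 7.7 | 4.1 |
| 0.13, 1.00 | 17.2 | 5.5 | 4.5 |
| 0.32, 1.00 | 15.1 | 7.9 | 5.6 |
| 0.57, 0.69 | 5.7 | 12.6 | 5.0 |

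If all enter below 3 per week, the change test gives 6.9-8.7% and rank ANCOVA 4.7-5.5%. These excesses are offset elsewhere. With 17.2% in 13.4% of trials and 5% overall, the remaining trials run at (5.0 - 0.134 × 17.2)/0.866 = 3.1%.

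**Interval width** (Hodges-Lehmann, stools per week, unrestricted entry at the low correlations). Change / 7-day alone / adjusted: 2.09/1.81/1.81, 1.90/1.80/1.74, 1.97/1.54/1.50, 1.76/1.50/1.45. Adjusted intervals are 8-24% narrower than those for change, but only 0-3% narrower than those for the 7-day value. At low correlation, then, most of the benefit comes from not subtracting baseline.

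**The case against.** The strongest reply is that nothing here is an error. The comparison is randomised and the Mann-Whitney test keeps its level. If improvement means change, baseline is already used. No power figure belongs to this trial, and at high correlation the planned test does slightly better. Frequency baseline is one recalled weekly item set against a daily diary, and entry below 3 per week would narrow its spread. The visible diary has no stool-count column, and the answer format of Appendix D question 1 cannot be seen.

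Most of this stands, and it limits the point to precision and reporting. It does not touch the missing estimate and interval, which need no assumed correlation. A noisy recalled baseline favours estimating the correction over subtracting in full. The data questions apply equally to the planned improvement score, which needs the same two values.

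A reader might infer that the planned test has an inflated false-positive rate. The plan does not support that: the 6-17% range applies only to trials with a sizeable chance imbalance, and the average over all trials is near 5%. A reader might also infer that entry route alone decides the gain. It does not: with unrestricted entry, the gain changes sign with correlation, SD ratio and baseline reliability.

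**Conclusion.** A cheap improvement. The firm part is the absence of a between-arm estimate and interval for both stool outcomes, together with an undefined improvement score.

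The case for adjustment is conditional. At an assumed 75 per arm and rate ratio 1.35, with improvement read as change, the frequency gain over the planned test runs from about -5 to about +20 points:
- large at low correlation with unrestricted entry;
- about 1 to 5 points if all enter below 3 per week;
- about 2 to 5 points lost in most settings with correlation above about 0.5-0.6.

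Against the 7-day value alone, adjustment adds 0 to 4 points at low correlation and about 6 to 16 at high. In the roughly 13-16% of trials with a baseline difference above 1.5 SE, the change test rejects falsely in about 6-17% (unrestricted entry) and rank ANCOVA in about 4-6%.

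It would be tempting to conclude that this trial forfeits up to 20 points of power. The documents cannot support that, since sample size, effect, SDs and correlation are all absent.

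**What to change.** 1. State which recorded values are the baseline and the 7-day value for each outcome, including the time window of the BEFORE row and the source of the daily stool count. Define improvement from them. For consistency, say which direction of movement on the Bristol scale counts, as the plan does not.
2. Report the between-arm difference in each outcome with a 95% confidence interval.
3. Compare the 7-day value between arms adjusted for its own baseline by rank ANCOVA (Quade): rank follow-up and baseline over both arms, regress one on the other, and compare residuals. Build the interval to match, for example Hodges-Lehmann on baseline-adjusted residuals, or take estimate, interval and p-value together from an ANCOVA or proportional-odds model. Rank ANCOVA alone gives only a p-value, and an unadjusted interval could disagree with it. In the simulations the unadjusted interval was conservative (coverage 99-100%, against 93-98% adjusted).
4. The SAP is in the past tense. If the analysis is done, report items 2 and 3 as supplementary.

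Cost: two or three sentences of SAP text, a few lines of analysis and no new data. The statistical downside is a few power points against the change score if correlation proves high.

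### Daily five-level symptom scores in the primary end point are compared by an unspecified chi-squared test, with no BEFORE-score covariate and no rule for turning seven days into one value

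*Combined protocol and SAP*

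**What the plan says.** Section 8.1 lists, within the primary end point, "constipated related symptoms scoring/day over the period of 7 study days", next to stool output and stool consistency. Section 9.1 gives the scale: "Severity of symptom is measured by Likert score of frequency (Very frequently, frequently, occasionally, rarely and never". Section 9.2 has patients complete a stool chart and says they "recorded their symptoms in a given dairy daily during the study period". The diary in Appendix B has a BEFORE row and rows for days 1 to 7, with columns for straining, painful evacuation, bloating and flatulence, stomach cramps, and others.

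The third paragraph of the SAP gives the whole analysis of these scores: "The constipation-related symptom improvements were analysed using the chi-squared test". The sentence before it treats the companion outcomes differently: "improvement in stool frequencies and stool consistency between the treatment and placebo group were compared using the Mann-Whitney U test". Baseline data appear in the SAP only as a comparison of characteristics between arms.

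**The concern.** The sentence leaves four things open: the version of the test, the layout of the table, the definition of improvement, and the value or values taken from the seven days. The natural Pearson readings both waste information. A 2x5 table treats five ordered levels as unordered labels, and an improved/not improved table counts a one-level and a four-level change alike. A trend version keeps the order, but none is named. No version carries the BEFORE score as a covariate, although the diary collects it.

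Two things are at stake. A real shift in a component of the primary end point is more likely to be missed than it need be. And because improvement is undefined, the reading could be settled after the data are seen.

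**Working it through.** **Inputs from the documents.** Five ordered levels (section 9.1); one BEFORE value and seven daily values (Appendix B); significance at 0.050 with sidedness not stated (SAP). Section 6 mentions 10% drop-out and a sample size calculation, but no sample size, power, effect size or score distribution is given. There is therefore no figure to reproduce, and everything below rests on assumptions.

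**Step 1: cost of ignoring order (no baseline).** A 1-df test with 80% power at two-sided 5% has noncentrality (1.960 + 0.842)² = 7.85. The same noncentrality on 4 df gives 59.5% power. Restoring 80% takes 1.52 times the patients.

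Worked case: assumed control distribution 20% per level, odds ratio 2.0.
- Ordinal test, per arm: 6 × 7.85 / [(ln 2)² × (1 − Σp̄³)] = 47.1 / (0.480 × 0.955) ≈ 103, where p̄ is the mean of the two arms' level proportions.
- Pearson 2x5: Σ(p − q)²/(p + q) = 0.0743 per patient per arm. The noncentrality needed on 4 df is 1.52 × 7.85 ≈ 11.9, so n ≈ 161 per arm, and 161/103 = 1.56.

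Over three assumed distributions and odds ratios of 2.0 and 2.5, Pearson 2x5 has 57–58% power where the ordinal test has 80%. A two-category split has 24–70%, depending on the cut.

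**Step 2: day-7 scores, with and without BEFORE.** Simulation model: normal latent scores for BEFORE and days 1–7, cut at 15/20/30/20/15%; 75 per arm; shift 0.41 SD; BEFORE-day correlation r; between-day correlation ρ; placebo improvement 0 or 0.5 SD; effect either sustained over days 1–7 or building up linearly to day 7. That makes 20 settings of 1,500 trials each. Monte Carlo error is at most 1.96 × √(0.25/1500) = 2.5 points. Power (%), sustained effect:

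| r, ρ | Placebo | Improved/not | 2x5 | Trend | Rank ANCOVA with BEFORE |
|---|---|---|---|---|---|
| 0.3, 0.5 | 0 | 35.7 | 43.3 | 66.6 | 69.5 |
| 0.5, 0.6 | 0 | 45.3 | 44.1 | 66.1 | 74.6 |
| 0.7, 0.8 | 0 | 62.8 | 45.3 | 65.7 | 87.7 |
| 0.3, 0.5 | 0.5 SD | 30.5 | 42.0 | 63.3 | 66.3 |
| 0.7, 0.8 | 0.5 SD | 48.8 | 39.6 | 61.9 | 81.5 |

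Over all settings and repeat runs: improved/not about 29–64%, 2x5 38–48%, trend 62–69%, rank ANCOVA 64–88%. Setting by setting, the loss against rank ANCOVA is 24–37 points (improved/not), 23–44 points (2x5) and 2–22 points (trend).

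A variant with other inputs (60 per arm, 0.45 SD, correlation 0.5) gives 44% improved/not, 41% for 2x5, 66% for Mann-Whitney on day 7 and 75% for baseline-adjusted ANCOVA on day 7.

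**Step 3: which days to summarise.** Rank ANCOVA with BEFORE, compared in the same run:

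| Effect | Days 1–7 mean | Days 4–7 mean |
|---|---|---|
| Sustained | 80–97% | 76–96% |
| Building up | 38–60% | 62–84% |

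The later window costs at most 4 points if the effect is sustained and gains 21–26 points if it builds up. Under build-up, the days 1–7 mean can fall below a Pearson test on day 7.

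**Step 4: type I error.** With no effect, each test fixed in advance rejected 3.5–6.8% over 20 settings. Taking the smallest p-value among three readings (day-7 improved/not, day-7 2x5, 7-day mean improved by at least one level) rejected 12–15%. Seven plausible chi-squared readings gave 20–22%.

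**The case against.** **The test may be a trend test, and improvement may already use baseline.** Both are possible. Under a trend test the ordering loss disappears, and what remains is the missing adjustment: 2–22 points, small when BEFORE correlates weakly with later days. A reader might infer that baseline is ignored altogether. The documents do not support that, because improvement implies comparison with BEFORE. But subtracting or dichotomising is not adjusting: at r = 0.3 with a sustained effect, Mann-Whitney on the change score has 41–50% power against 66–71% for rank ANCOVA.

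**A proportion improved is a legitimate target.** It is, and part of the gap reflects a different target. It is worth keeping as a secondary summary.

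**The size is assumed.** This stands. On the 7-day mean, at 100 per arm and 0.6 SD, improved/not has 91–95% against 100%; at 40 per arm and 0.25 SD it has 15% against 34–36%.

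Two stronger readings should be resisted:
- A reader might infer that most daily scores would be empty, since patients entering with under three movements a week have few evacuations. But the entry criterion in section 4.2 is "Infrequent bowel movements of fewer than three bowel movements per week or difficult passage of stools", so infrequency is only one route in. It also describes entry rather than study days, and it has no bearing on bloating or cramps.
- A reader might infer conflicting scales from the diary header, "LIKERT SCALE / NUMERIC PAIN RATING SCALE". The diary instruction is plain, "Please fill up the boxes according to likert scale for the constipation related symptoms", and the header may label a graphic lost in text extraction.

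**Conclusion.** The point holds as a matter of efficiency and specification, and it should be fixed. Under any reading, the planned comparison omits adjustment for a BEFORE score the trial already collects; under a Pearson reading it also discards order or size of change. The direction was the same in every setting examined. The size rests wholly on assumed sample size, shift, score distribution and correlations.

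A reader might go further and call the test invalid, or conclude that type I error is untouched. Neither follows. A single test fixed in advance holds 5%, whereas an undefined improvement permits a choice after the data are seen, and that would not. The documents do not show that such a choice was made. The SAP is written in the past tense, so the analysis may already have been done.

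**What to change.** Replace the symptom sentence in the SAP with:

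> For each diary symptom, the mean score over days 4–7 will be compared between arms by rank ANCOVA with terms for arm and the BEFORE score. Sensitivity analyses: the days 1–7 mean, day 7 alone, and a repeated-measures ordinal model over days 1–7 with the BEFORE score. Secondary summary: proportion improved (days 4–7 mean at least one level below BEFORE), with risk difference and 95% CI. The symptom p-values will be adjusted across symptoms by Holm.

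State that the levels are coded with never as the lowest, so that lower means better. Report by arm the number of days with a recorded score for straining and painful evacuation. Do not build the main analysis on a rule that leaves days without evacuation unscored: stool output is itself in the primary end point, and treatment may change it, so such a rule would select days differently by arm.

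Costs:
- No new data are needed.
- Averaging treats the levels as equally spaced; the repeated-measures ordinal model checks this.
- The days 4–7 window gives up a few points of power against days 1–7 if the effect is present from day 1.
- The power figures above are for one symptom at 5%. Holm over the four named symptoms starts at 0.05/4 = 0.0125, so some of the gain is given back.
- If the data have already been analysed, this analysis must be labelled post hoc.
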